9.2. Adverse Events of Special Interest

Adverse events of special interest as listed below will be summarized by treatment group.

The AE of special interest:

- Neutropenia (or Neutrophil count decreased)
- Hepatotoxicity

The number and percentage of subject who experience any TEAE of special interest and the number of events will be presented for each preferred term in a descending order of frequency within treatment groups from high dose to low dose and placebo group.

A listing of AE of special interest will be provided with verbatim term, PT and SOC presented, as well as other relevant event attributes collected on CRF.

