6.4.5.5 Reporting Serious Adverse Events

Any AE that meets SAE criteria (Section 6.4.5.2) must be reported to PPD Pharmacovigilance (PVG) immediately (ie, within 24 hours) after site personnel are aware of the event. This must be done via the eCRFs on the AE page. The entry will automatically be

sent to the PPD PVG team for review. If the eCRF system is unavailable, a manual SAE form may be used and faxed to the numbers outlined below.

The nonserious adverse event of special interest (AESI) defined in Section 6.4.5.6 should be recorded in the eCRF using the same process as for reporting SAEs.

The following contact information is to be used for PPD PVG:

PVG [contact]/[contact]

PVG Fax line: [contact]/[contact] or [contact]

6.4.5.6 Suspected Unexpected Serious Adverse Reactions and Nonserious Adverse Events of Special Interest

The following nonserious AESI should be recorded on the eCRF using the same process as for reporting SAEs.

- **Neutropenia** with fever defined as ANC <1500/mm³ or <1.5 × 10⁹/L on the most recent complete blood count with fever equal to or greater than 38°C that does not fulfill any of the serious criteria, ie, hospitalization.
- **Hepatotoxicity** defined as ALT >3 × ULN plus total bilirubin >2 × ULN that does not fulfill any of the serious criteria, ie, hospitalization. This information should be recorded on the drug induced liver injury eCRF each time the elevated laboratory parameters are met during the study.

Oscotec Inc. will promptly evaluate all suspected unexpected serious adverse reactions (SUSARs) and nonserious AEs of special interest against cumulative product experience to identify and expeditiously communicate possible new safety findings to Investigators, institutional review board (IRBs)/independent ethics committee (IECs), and applicable health authorities based on applicable legislation.

To determine reporting requirements for single AE cases, Oscotec Inc. will assess the expectedness of these events using the study drug Investigator's brochure. Reporting requirements will also be based on the Investigator's assessment of causality and seriousness, with allowance for upgrading by Oscotec Inc. as needed.

Osco Inc. will compare the severity of each SUSAR and the cumulative event frequency reported for the study with the severity and frequency reported in the applicable reference document.

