9.3. Clinical Laboratory Evaluations

The laboratory values will be graded using National Cancer Institute's Common Terminology Criteria for Adverse Events (CTCAE) version 5.0. For hematologic and chemistry laboratory values that fall outside of the grade criteria of CTCAE version 5.0, the grade of 0 will be assigned.

Summary statistics of baseline value, observed values and change from baseline at each schedule visit in the continuous hematology and clinical chemistry parameters will be provided by treatment group. Numeric values reported as less than (<) or greater than (>) a laboratory-defined limit will be included with the "<" or ">" signs ignored. Frequency summaries of shifts from baseline grade to the post-baseline grade at each schedule visit, and to the worst post-baseline grade during 12-week treatment period will be provided in the laboratory tests with CTCAE gradings. In addition, frequency summaries of shifts from baseline category to the post-baseline category in terms of normal/abnormal will be provided over time in other laboratory parameters.

Subject data listings of all laboratory data sorted by subject identifier, date of collection and laboratory parameter will be provided based on the safety set, with abnormality indicated.

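### SAP 9.2 does not tabulate the adverse events of special interest that Protocol 6.4.5.6 defines: the neutropenia item is broader, and the liver item has no selection rule

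*SAP*

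**What the plan says.** Protocol 6.4.5.6 defines two AESIs by criteria:

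- **Neutropenia with fever:** ANC <1500/mm³ "on the most recent complete blood count with fever equal to or greater than 38°C that does not fulfill any of the serious criteria".
- **Hepatotoxicity:** ALT >3 × ULN "plus total bilirubin >2 × ULN that does not fulfill any of the serious criteria". For this event the protocol adds: "This information should be recorded on the drug induced liver injury eCRF each time the elevated laboratory parameters are met during the study".

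Both are limited to nonserious events, and the recording route is set out: "The following nonserious AESI should be recorded on the eCRF using the same process as for reporting SAEs".

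SAP 9.2 lists the AESIs as "Neutropenia (or Neutrophil count decreased") and "Hepatotoxicity". The number and percentage of subjects with "any TEAE of special interest and the number of events will be presented for each preferred term". The section gives no threshold, does not refer to Protocol 6.4.5.6 and does not mention the liver injury eCRF.

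For laboratory data, SAP 9.3 provides "Frequency summaries of shifts from baseline grade to the post-baseline grade at each schedule visit", shifts to the worst grade on treatment, descriptive summaries, and listings of all values by subject, collection date and parameter. SAP 14 declares no changes to the planned analysis.

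**The concern.** The AESI table is where a reader looks for the events that the protocol singled out. If its rows are filled by a different rule, its counts by arm do not answer the protocol's question, and nothing in the SAP warns the reader.

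This matters more than usual in this trial. Protocol 1.5 names immune system effects and liver enzyme changes among the potential risks. Protocol 6.4.4 adopts the FDA guidance on drug-induced liver injury for assessing liver tests. Protocol 1.3 says that 400 mg BID has not been studied in humans before. Protocol 6.7 and 11.1.1 plan no safety or data monitoring committee. The end-of-study safety tables therefore carry much of the comparison between doses.

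**Working it through.** No arithmetic applies, and the plan states no figure to reproduce. The check sets the two definitions side by side, then looks for any other SAP table that would close the gap.

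**Step 1. Definitions.**

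| Element | Protocol 6.4.5.6 | SAP 9.2 |
|---|---|---|
| ANC limit | <1500/mm³ on the latest blood count | none stated |
| Fever | at least 38°C required | none stated |
| Liver limits | ALT >3 × ULN plus total bilirubin >2 × ULN | none stated |
| Seriousness | nonserious only | no restriction |
| Liver data source | AE page and liver injury eCRF | TEAEs; eCRF not mentioned |

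**Step 2. Which subjects each rule counts.** Protocol 6.4.5.2 reserves the AE term neutropenia for ANC <1500/mm³, with or without fever. Applying both rules to typical cases gives:

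| Case | Protocol AESI? | Counted under SAP 9.2? |
|---|---|---|
| A. ANC <1500/mm³, no fever, reported as neutropenia | no | yes |
| B. As A with fever of at least 38°C, nonserious | yes | yes, not distinguishable from A |
| C. As B but serious | no (reported as an SAE) | yes |
| D. ALT and bilirubin both over their limits, nonserious, reported as hepatotoxicity | yes | yes |
| E. Same values as D, nonserious, but coded as separate laboratory terms or another liver term | yes | not stated |

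Cases A and C show that the SAP's neutropenia count is at least as large as the protocol's for events reported under that term, and exceeds it whenever an afebrile or serious case occurs. Case E turns on a rule that the SAP does not give. Investigator judgment adds to the uncertainty: under Protocol 6.9 an abnormal laboratory result becomes an AE when the investigator considers it clinically significant, whereas the AESI definition is purely numerical.

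**Step 3. Other SAP tables.**

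- SAP 9.1 tabulates all TEAEs by system organ class and preferred term. It shows the separate terms but does not link them within a subject.
- SAP 9.3 describes shifts by laboratory test. It includes no joint summary of ALT and bilirubin.
- SAP 9.4 gives a normal range for oral temperature but leaves temperature out of its shift tables, so fever is not counted there.

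No summary table described in SAP 9.1 to 9.4 counts subjects by either protocol definition.

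**The case against.** The strongest reply has four parts.

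1. *The preferred-term wording describes how results are laid out, not how events are selected.* This stands. SAP 9.2 may intend each item as a group of terms; the first already names two. A reader might infer that a liver case coded under separate terms is certainly left out. The text does not support that. It supports only that no selection rule is stated and that omission is possible.

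2. *The data are not lost.* This also stands. A reader might infer that no output shows ALT and bilirubin together. In fact the SAP 9.3 listings put values from one draw under the same subject and date, and SAP 9.2 adds an AESI listing. What is missing is a summary count by arm.

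3. *A liver count of zero would need several departures.* Protocol 6.4.5.6 gives sites the name hepatotoxicity, the SAE reporting process and a dedicated eCRF, and has the sponsor evaluate AESIs promptly. So it would be wrong to say that the table will read zero, or that detecting a signal during the trial depends on it. But the SAP does not say that the AESI record or the liver eCRF feeds the table, so these safeguards are not part of the analysis as written.

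4. *The protocol promises no such table, and a broader set is a defensible choice.* Protocol 7.7.5 indeed commits to no AESI analysis. A broader neutropenia summary is reasonable if labelled as one. Under the AESI heading, with no note that fever and seriousness were dropped, it will be read as the protocol's event. Breadth is also no defence for the liver item, where an undefined term can be narrower than the criteria.

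**Conclusion.** The point holds in a limited form and should be corrected. Followed as written, SAP 9.2 gives an AESI count that does not match Protocol 6.4.5.6.

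- **Neutropenia:** over-counting follows directly from the text, whenever an afebrile or serious case is reported under the listed terms.
- **Liver:** under-counting is possible, not certain. It depends on how sites report, how terms are coded and how the programmer reads a section with no rule.

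The documents give no expected frequency for either event, so no numerical size can be attached. The table is descriptive. The primary analysis, power and the underlying safety data are unaffected, and individual cases can still be found by hand in the listings. The defect lies in the count by arm.

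**What to change.** Rewrite SAP 9.2 so that both AESIs are derived from the Protocol 6.4.5.6 criteria:

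- **Liver:** flag subjects with ALT >3 × ULN plus total bilirubin >2 × ULN, using the laboratory data (including local results, which Protocol 6.4.4 allows for AE assessment) and the liver injury eCRF. State the time window within which the two elevations count as concurrent. The protocol gives none, and a requirement that both come from one sample would be narrower than its wording.
- **Neutropenia:** flag subjects with fever of at least 38°C, from recorded temperature or from fever reported as an AE, whose latest blood count shows ANC <1500/mm³. Visit temperatures alone would miss fever between visits.
- **Seriousness:** show serious and nonserious cases meeting the criteria in separate rows. The nonserious row then matches the protocol AESI, and no serious case is hidden.
- **Supportive output:** keep the preferred-term tables, labelled as broader term groupings, and list the terms in each group.

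Record the definitions before database lock. The cost is a few derived flags and one added table, all from data already collected. The main work is agreeing the concurrence window and the rule linking fever to the blood count.

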9.3. Clinical Laboratory Evaluations

The laboratory values will be graded using National Cancer Institute's Common Terminology Criteria for Adverse Events (CTCAE) version 5.0. For hematologic and chemistry laboratory values that fall outside of the grade criteria of CTCAE version 5.0, the grade of 0 will be assigned.

Summary statistics of baseline value, observed values and change from baseline at each schedule visit in the continuous hematology and clinical chemistry parameters will be provided by treatment group. Numeric values reported as less than (<) or greater than (>) a laboratory-defined limit will be included with the "<" or ">" signs ignored. Frequency summaries of shifts from baseline grade to the post-baseline grade at each schedule visit, and to the worst post-baseline grade during 12-week treatment period will be provided in the laboratory tests with CTCAE gradings. In addition, frequency summaries of shifts from baseline category to the post-baseline category in terms of normal/abnormal will be provided over time in other laboratory parameters.

Subject data listings of all laboratory data sorted by subject identifier, date of collection and laboratory parameter will be provided based on the safety set, with abnormality indicated.

9.4. Vital Sign Measurements

Vital sign measures will include sitting systolic and diastolic blood pressures (mmHg), pulse rate (beats/ minute), respiratory rate (breaths/ minute) and oral temperature (°C).

Summary statistics of baseline, observed value and change from baseline will be provided by treatment group over time. Frequency summaries of shift from baseline to post-baseline visits by normal indicator (in terms of low, normal and high) will be provided for pulse rate, respiratory rate and blood pressure. The normal ranges are defined as: 60 to 100 beats/minute for pulse rate, 12 to 20 breaths/minute for respiratory rate, 36.5 to 37.5 °C for oral temperature, 90 to 140 mmHg for systolic blood pressure, and 60 to 90 mmHg for diastolic blood pressure. The low

abnormality is defined as any value lower than the low limit of normal range, and the high abnormality is defined as any value higher than the high limit of normal range.

A subject data listing of all vital signs data will be presented by subject identifier, date of collection and vital sign parameter, with abnormality indicated.

9.5. Physical Examination

Physical examination is only performed at screening, baseline, end-of-treatment and end-of-study. A subject data listing of physical examination will also be presented with examination visit, study day, system organ class examined and the examination results.

9.6. Electrocardiogram

Single 12-lead ECGs will be obtained, after the subject has been in the supine position for at least 5 minutes, prior to randomization at Day 1 and at subsequent visit as indicated in the schedule of events. ECG parameters include RR interval, PR interval, QRS width, QT interval, and corrected QT interval from Fridericia's formula (QTcF). In addition, the 12-lead ECG results will be interpreted by the investigator and recorded as: normal; abnormal not clinically significant; or abnormal clinically significant.

Summary statistics of observed values and changes from baseline in ECG parameters will be provided over time. Frequency summaries of shifts from baseline interpretation results to post-baseline interpretation results at each visit will be provided. The number and percentage of subjects who have the following QTcF interval prolongation will be tabulated by treatment group over time. The descriptive summary of QTcF interval for the subjects with each specific interval prolongation will also be presented.

- QTcF > 450 msec
- QTcF > 480 msec
- QTcF > 500 msec

A subject data listing of ECG measurements will be provided by subject identifier, date of collection and ECG parameters.

10. Pharmacokinetic Analysis

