Intolerable nausea or vomiting	First	Study drug may be withheld and then restarted at a reduced dose by skipping one of the doses.

AE	Occurrence ^b	Action
	Second	Discontinue study drug permanently if the intolerance reoccurs or persists.
QTcF >500 ms for female subject OR >480 ms for male subject, at any time point	-	
The ECG should be repeated as triplicate (all three within 2 minutes) and a cardiology consult may be obtained as medically necessary.
 
 • If the repeat ECG confirms QTcF >500 ms (females) or >480 ms (males), dosing must be interrupted for up to 14 days • If the QTcF resolves to ≤480 ms (males and females)/they may resume dosing at the reduced dose by skipping one of the doses (ie, morning or evening) • If the QTcF remains >480 ms (males and females) after 14 days of dose interruption, the study drug must be permanently discontinued.
QTcF change of >30 ms from baseline	-	If the QTcF has increased >30 ms when compared to the baseline with no other known etiology, and the PI considers it clinically significant then a confirmatory ECG (single) will be performed and dose should be reduced by skipping one of the doses (ie, morning or evening) for the remainder of the study.

Abbreviations: ACE, angiotensin-converting-enzyme; AE, adverse event; ALP, alkaline phosphatase; ALT, alanine aminotransferase; ANC, absolute neutrophil count; AST, aspartate aminotransferase; csDMARDs, conventional synthetic disease-modifying antirheumatic drugs; ECG, electrocardiogram; MOA, mechanism of action; PI, principal investigator; QTcF, QT interval correction for heart rate (QTc) using Fridericia's correction formula; ULN, upper limit of normal

- ^a These are examples based on previously observed AEs for agents with similar MOA (ie, fostamatinib). All other potential/spontaneous Grade 3/4 AEs that can warrant dose reduction or interruption are not excluded and will be assessed on an ongoing basis during the study. Those would be evaluated upon judgment by the principal Investigator and the safety operations team.
- ^b First/second occurrence relates to AE; abnormalities at repeat tests during monitoring of an AE are considered to belong to the same event (AE).
- c A central laboratory must be used for repeat ALT, AST, ALP or ANC.

Subject Error

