5. Subject who has any condition that could confound the evaluation of the data or the effect of the study drug, such as:

- a. Any other inflammatory or rheumatic diseases, including but not limited to psoriatic arthritis, ankylosing spondylitis, spondyloarthritis, systemic lupus erythematosus, Lyme disease, or uncontrolled fibromyalgia. Subjects with inactive or well-controlled fibromyalgia will be allowed to be enrolled in this study if the disease does not impact the study assessments, as per the investigator's judgement. Subjects with Sjogren's disease secondary to RA are eligible.
- b. Any conditions significantly affecting the nervous system (ie, neuropathic conditions or nervous system damage) if it may interfere with the investigator's assessment on DAS including joint counts.
- c. Severe physical incapacitation (unable to perform routine self-care, has RA ACR functional status class 4 [Arnett et al 1988], or who cannot benefit from medication).
- d. Any other serious acute or chronic medical or psychiatric condition that may increase the risk associated with study participation or study drug administration or that may interfere with the interpretation of study.

6. Subject who currently has one or more of the following medical conditions which in the opinion of the investigator would put the subject at risk by participating in the protocol:

- a. Uncontrolled diabetes mellitus, even after insulin treatment.
- b. Uncontrolled hypertension (as defined by systolic blood pressure ≥ 160 mm Hg or diastolic blood pressure ≥ 100 mm Hg on >1 occurrence or as judged by the investigator).
- c. Clinically significant finding meeting any protocol exclusion criteria on chest x-ray. Chest x-ray must be obtained during the screening period, unless a radiograph lung imaging (ultrasound not acceptable) was obtained within 12 weeks prior to the screening visit.
- d. Evidence of cardiac conditions as defined by the following:
 - New York Heart Association (NYHA) class III or IV heart failure, severe uncontrolled cardiac disease (unstable angina), or myocardial infarction within the 6 months prior to Day 1.

- Clinically relevant or significant ECG abnormalities, including ECG and QT interval correction for heart rate (QTc) using Fridericia's correction formula (QTcF). Subject with prolonged QT interval (using QTcF) defined as QTc >450 ms for male and >470 ms for female at retest will be excluded at screening.

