6.4.5.2 Serious Adverse Events

An SAE is defined as any event that results in death, is immediately life-threatening, requires inpatient hospitalization or prolongation of existing hospitalization, results in persistent or significant disability/incapacity, or is a congenital anomaly/birth defect.

Important medical events that may not result in death, be life-threatening, or require hospitalization may be considered SAEs when, based upon appropriate medical judgment, they may jeopardize the subject or require medical or surgical intervention to prevent one of the outcomes listed in this definition. Examples of such medical events include an allergic bronchospasm requiring intensive treatment in an emergency room or at home, blood dyscrasias, convulsions that do not result in inpatient hospitalization, or the development of drug dependency or drug abuse.

Note: The AE terms neutropenia and hypertension should be used only when reporting events that meet the following criteria:

- The term neutropenia is reserved for reporting an absolute neutrophil count (ANC) $<1500/\text{mm}^3$ or $<1.5 \times 10^9/\text{L}$ and may or may not be associated with fever or concurrent infection.
- The term hypertension is reserved for reporting an increase in systolic blood pressure $>160 \text{ mm Hg}$, or diastolic blood pressure $>100 \text{ mm Hg}$, or any clinically significant increase in blood pressure that requires modification of the subject's antihypertensive regimen.

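### SAP 9.6 counts QTcF outliers only as absolute values with the sexes pooled, so it includes eligible women who never changed and has no count of rises above 30 ms

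*SAP*

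**What the plan says.** **QTcF in the SAP.** SAP 9.6 states: "The number and percentage of subjects who have the following QTcF interval prolongation will be tabulated by treatment group over time". The rows are "QTcF > 450 msec", "QTcF > 480 msec" and "QTcF > 500 msec". The section names no sex split, no condition on baseline and no category of change. Besides this table it plans descriptive statistics of observed values and of changes from baseline, shift tables of the investigator's ECG interpretation, and a listing.

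**QTcF in the protocol.** Protocol 4.1.2 (item 6d) excludes subjects with a prolonged interval, "defined as QTc >450 ms for male and >470 ms for female at retest". Table 3-1 in Protocol 3.1.1 has two QTcF rows. One is absolute and differs by sex: above 500 ms for women and above 480 ms for men. The other is relative: "If the QTcF has increased >30 ms when compared to the baseline with no other known etiology", with the further condition that the investigator judges the change clinically significant.

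**Blood pressure.** SAP 9.4 plans change-from-baseline statistics and also "Frequency summaries of shift from baseline to post-baseline visits by normal indicator (in terms of low, normal and high"), with 140 and 90 mm Hg as the upper limits of normal. Table 3-1 uses sustained values above 140/90 for antihypertensive treatment, and sustained values above 170/100 in previously normotensive subjects for the study drug. Protocol 6.4.5.2 adds: "The term hypertension is reserved for reporting an increase in systolic blood pressure" above 160 mm Hg or diastolic pressure above 100 mm Hg, or a clinically significant increase that leads to a changed antihypertensive regimen.

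**The concern.** An outlier table in the safety section should show how many subjects per arm moved into a range of interest while on treatment. The QTcF table mixes that with where subjects started. Its lowest row lies inside the range in which women may enter, so part of the count can be entry status. In the other direction, a clear rise from a low starting value need not reach any row.

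The table matters more here than in many Phase 2 trials. Protocol 1.5 names cardiovascular effects as a potential risk. Protocol 1.3 says that 400 mg BID had not been given to humans before. Sections 6.7 and 11.1.1 plan neither a safety monitoring committee nor an external data monitoring committee. The final tables are therefore the main comparison of these risks between arms.

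**Working it through.** The plan states no figure to reproduce on this point. The check classifies pairs of baseline b and post-baseline value y, in whole ms, by the SAP rows and by the Table 3-1 rows. It assumes that b lies within the eligibility limit (at most 450 ms for men, 470 ms for women).

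1. **No change but counted.** This needs y = b and y > 450. For women, b = 451 to 470 qualifies. For men, no eligible b does. Example: a woman at 460 ms throughout has change 0 and is in the >450 row at every visit.

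2. **Rise above 30 ms but not counted.** This needs y − b > 30 and y ≤ 450, so b + 31 ≤ y ≤ 450, which gives b ≤ 419, in either sex. Example: 400 to 435 ms is +35 ms and enters no row. From 390 ms, rises up to 450 − 390 = 60 ms enter no row.

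3. **Absolute Table 3-1 limits.** Every man above 480 ms and every woman above 500 ms falls in the SAP row with that same number. An enumeration of b from 350 ms to the eligibility limit and y from 350 to 560 ms confirms this: 8,080 of 8,080 such pairs for men and 7,260 of 7,260 for women fall in a row. On the same grid, 2,485 pairs in each sex rise by more than 30 ms and enter no row, all with b from 350 to 419 ms. These numbers show which cases are possible, not how often they occur.

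4. **Pooling.** Let M and F be the numbers of men and women above a given value. The SAP gives M480 + F480 and M500 + F500. The number at the protocol's absolute limit is M480 + F500, which equals the >480 row minus the women at 481 to 500 ms. The pooled table does not give that last number. The two rows only bound the answer, which lies between the >500 count and the >480 count.

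5. **Possible size of item 1 (assumption).** The documents give no QTcF distribution. If eligible women's baseline QTcF were normal with mean μ and SD σ, truncated at 470 ms, the share at 451 to 470 ms would be [Φ((470 − μ)/σ) − Φ((450 − μ)/σ)] / Φ((470 − μ)/σ):
   - μ = 415, σ = 18: 0.025
   - μ = 420, σ = 20: 0.061
   - μ = 425, σ = 18: 0.077

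   In an arm of 37 made up entirely of women, that is 37 × 0.025 = 0.9 to 37 × 0.077 = 2.8 subjects, and fewer in a mixed arm.

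6. **Blood pressure.** Protocol 4.1.2 excludes repeated values of 160 or more systolic, or 100 or more diastolic. Baselines of 141 to 159 or 91 to 99 mm Hg can therefore enter, and SAP 9.4 already classes them as high. From there, a rise above 160/100 or 170/100 shows only as high-to-high. If normotensive means at most 140/90 (the protocol does not define it), a normotensive subject who passes 170 or 100 shows as normal-to-high, pooled with values of 141 to 170 or 91 to 100.

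**The case against.** Much can be said for the SAP. A reader might infer three stronger criticisms, and the documents support none of them.

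- *The tables ignore change from baseline.* They do not. SAP 9.4 and 9.6 both plan change-from-baseline statistics, the blood-pressure table is itself a baseline shift table, and SAP 9.6 adds shifts in ECG interpretation. SAP 4.1 includes the minimum and maximum in continuous summaries, so the largest rise at each visit is visible. Only the number of subjects with such a rise is absent.
- *The limits are not the protocol's.* 480 and 500 ms are the absolute QTcF limits of Table 3-1, and 140/90 is one of its blood-pressure limits.
- *Subjects at the absolute limits are missed.* Step 3 shows that none is missed for QTcF. The row at 170/100 covers only sustained elevation in previously normotensive subjects, and step 6 shows that these appear in the shift table under the stated reading of normotensive.

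Two further points count against the concern. The 30 ms rule also needs the absence of another cause and a judgment of clinical significance, so a rise of 35 ms alone does not meet it. SAP 9.1 tabulates adverse events by preferred term, which would include reported hypertension, and events leading to treatment modification or discontinuation. Protocol 6.4.3 sends clinically significant ECG changes to the adverse event page. Finally, the table is descriptive, and randomisation balances baseline-driven counts in expectation.

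All of this stands and limits the point. It does not supply the missing count. A maximum shows one subject, and the adverse event tables show only what was judged and reported. Balance in expectation does not stop one or two unchanged subjects from blurring a comparison of small counts.

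**Conclusion.** The point holds as a cheap improvement to the QTcF outlier table, not as an error in the safety analysis. Three things follow from the documents alone. The >450 row can count women at 451 to 470 ms who never changed. The >480 row mixes men at their Table 3-1 limit with women at 481 to 500 ms who are not at theirs. A rise of more than 30 ms from 419 ms or lower that ends at or below 450 ms enters no count.

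How many subjects this affects cannot be derived from the documents. Under the assumed distributions the first item would be at most about 1 to 3 subjects per arm, and no estimate is possible for the third. The blood-pressure part is secondary: it concerns detail inside the high category, and the study's earlier evidence is modest. Protocol 1.1 reports a slight upward trend in the multiple-dose study, with no significant difference from placebo.

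**What to change.** In SAP 9.6:

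- Add, per arm, the number and percentage of subjects with a QTcF increase above 30 ms from baseline, by visit and at any post-baseline visit. Label it a numeric screen, because the Table 3-1 rule has further conditions.
- Show the 450, 480 and 500 ms rows separately for men and women, so that men above 480 ms and women above 500 ms can be read directly.
- In each row, count only post-baseline exceedances in subjects who were not above that limit at baseline, and use those subjects as the denominator.

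A row for rises above 60 ms is not needed on the strength of these documents, which use no such limit.

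Optionally, in SAP 9.4, add post-baseline counts above 160/100 and above 170/100 mm Hg, split by normal or high baseline. A footnote should say that they do not apply the protocol's condition that the rise be sustained.

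The cost is a few lines of SAP text and one or two more descriptive tables from data already collected. Counts will be small, more so once split by sex. No clinical rule changes.
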